14.3. Pharmacokinetic Analysis

The primary PK objective is to compare the PK of NKF-INS(A) to US-approved and EU-authorized insulin aspart to demonstrate PK similarity for insulin aspart. The secondary PK objective is to evaluate additional PK parameters of NKF-INS(A) compared to US-approved and EU-authorized insulin aspart. Details on the endpoints are provided in [Table 1](#).

PK concentrations and parameter data will be listed and summarized descriptively (N, arithmetic and geometric mean, SD, CV%, median, minimum, and maximum) by treatment group and graphically.

Biosimilarity between the test product and the US-approved and EU-authorized insulin aspart will be considered separately, i.e., test product vs US-approved product and test product vs EU-authorized product. Biosimilarity of the test and reference products will be assessed on the basis of the 90% Cis for estimates of the geometric mean ratios between the primary PK parameters of the test and reference products in relation to the conventional bioequivalence range of 80% to 125%. The test product will be compared to the reference product by means of statistical analysis with respect to the primary PK parameters using an analysis of variance after logarithmic transformation of the data. Point estimates and 90% Cis for the “test/reference” geometric mean ratios of these parameters will be provided. The primary PK parameters that will be used for the bioequivalence assessment are C_{max} and AUC_{0-t} . All other PK-related assessments of equivalence will be considered secondary.

Any missing samples or non-reportable concentration values will be disregarded in the PK analysis.

Refer to the SAP for full details.

14.4. Pharmacodynamic Analysis

The primary PD objective is to compare the PD of NKF-INS(A) to US-approved and EU-authorized insulin aspart injection by examining GIR profiles after a single SC dose. The secondary PD objective is to evaluate the additional parameters NKF-INS(A) compared to US-approved and EU-authorized insulin aspart. Details on the endpoints are provided in [Table 1](#). PD concentrations and parameter data will be listed and summarized descriptively (N, arithmetic and geometric mean, SD, CV%, median, minimum, and maximum) by treatment group and graphically.

As for PK similarity, biosimilarity between the test product and the US-approved and EU-authorized insulin aspart will be considered separately, i.e., test product vs US-approved product and test product vs EU-authorized product. Biosimilarity of the test and reference products will be assessed on the basis of the 95% Cis for estimates of the geometric mean ratios between the primary PK parameters of the test and reference products in relation to the conventional bioequivalence range of 80% to 125%. The test product will be compared to the reference product by means of statistical analysis with respect to the primary PD parameters using an analysis of variance after logarithmic transformation of the data. Point estimates and 90% and 95% Cis for the “test/reference” geometric mean ratios of these parameters will be provided. The primary PD parameters that will be used for the bioequivalence assessment are GIR_{max} and AUCGIR_{0-t} . All other PD-related assessments of equivalence will be considered secondary.

All PD analyses will be based on the PD Parameter Population. Refer to the SAP for full details.

14.5. Safety Analysis

All analyses of safety will be conducted on the Safety Population unless otherwise specified in the SAP.

All reported AEs will be graded using NCI CTCAE version 5.0 and will be coded using the Medical Dictionary for Regulatory Activities, version 26.0. The incidence of treatment-emergent AEs (TEAEs) will be included in incidence tables. Events with missing onset dates will be included as treatment-emergent. If a participant experiences more than 1 occurrence of the same AE, the occurrence with the greatest severity and the closest association with the study treatment will be used in the summary tables. All TEAEs will be summarized by treatment group (NKF-INS(A), US-NovoLog®, and EU-NovoRapid®) as follows:

- All AEs
- Grade ≥ 3 AEs
- AEs related to study treatment, including related Grade ≥ 3 AEs
- All adverse reactions
- SAEs

All AEs will be listed by participant, along with information regarding onset, duration, relationship and severity to study treatment, action taken with study treatment, treatment of event, and outcome.

Clinical laboratory data (hematology, clinical chemistry [including glucose], coagulation, and urinalysis) and vital signs (heart rate, respiratory rate, systolic and diastolic blood pressure, and temporal or ear temperature measurements) will be summarized by treatment group and

scheduled visits using descriptive statistics, including mean values and mean change from screening values, as well as numbers of participants with values outside limits of the normal range at each timepoint. Shift tables will be provided presenting change from screening values to the last EOS visit.

The frequency of ECG abnormalities (e.g., heart rate, PR interval, QRS complex, and QT-interval corrected by Fridericia's formula [Fridericia's corrected QT]) will be summarized by treatment group and scheduled visits using counts and percentages.

Participant ECG status (normal, abnormal clinically significant, or abnormal not clinically significant) may be summarized for each scheduled ECG and shifts from screening may be tabulated.

Injection site reactions will be summarized by treatment group and scheduled visits. The number and percentage of participants having reactions at each assessment timepoint, overall and by specific reaction subtype, will be presented.

Summary tables will be provided for concomitant medications initiated during the study period.

Clinically significant changes in physical examination findings and laboratory abnormalities will be listed as AEs.

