Safety	Safety assessments include vital signs, physical examinations, ECG recordings, clinical laboratory assessments (hematology, clinical chemistry [including glucose], coagulation, and urinalysis), AE monitoring (including injection site reactions). AEs will be coded by using the Medical Dictionary for Regulatory Activities dictionary. All treatment-emergent AEs (TEAEs) will be summarized by insulin product (NKF-INS(A), US-NovoLog®, EU-NovoRapid®) as follows: 
• All AEs• Grade ≥ 3 AEs• AEs related to study treatment, including related Grade ≥ 3 AEs• All adverse reactions• Serious AEs (SAEs) All AE data will be defined in the listing (onset, stop date, severity, etc.). The original results and change from baseline values for clinical laboratory assessments, vital signs, and ECG parameters, will be summarized by insulin product and scheduled visits. Potential clinically significant values will also be flagged and summarized. Significant changes in physical examination findings will be listed as AEs. Injection site reactions will be summarized by treatment group and scheduled visits. The number and percentage of participants having reactions at each assessment timepoint, overall and by specific reaction subtype, will be presented.
Other Assessments	Not applicable
Statistical Methods and Planned Analyses	The statistical evaluation will be performed using R version 4.0 or higher. All data will be listed, and summary tables and figures will be provided. Summary statistics will be presented by treatment group, to the extent possible. For continuous variables, data will be summarized with the number of participants (N), arithmetic mean, standard deviation (SD), median, minimum, and maximum by treatment group. Geometric mean and coefficient of variation (CV%) will be presented as appropriate, by treatment group. For categorical variables, data will be tabulated with the number and proportion of participants for each category by treatment group.
Interim Analysis	Not applicable.

Data Monitoring Committee	Not applicable.
----------------------------------	-----------------

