8.4. Treatment Modifications and Discontinuations

Dose reductions and adjustments are not permitted; any dose reductions and adjustments that occur will be recorded and considered protocol deviations.

Delays and omissions of study treatment administration because of medical or nonmedical reasons are not permitted. All delays and omissions of study treatment that occur during the study will be recorded and considered protocol deviations.

A participant may be discontinued from the study at any time for reasons including, but not limited to, the following:

- AE and/or SAEs in the judgment of the Investigator that may prevent the participant from continuing participation in the study.
- Participant withdrawal of consent (at any time, a participant's participation in the study may be terminated at their request).
- On the basis of the Investigator's clinical judgment.
- General or specific changes in the participant's condition that render them ineligible for further treatment according to the inclusion/exclusion criteria.
- Participant fails to adhere to the protocol requirements (e.g., study treatment noncompliance).
- Lost to follow up: the participant stopped coming for visits and study personnel were unable to contact the participant.

Note: In cases in which the participant is deemed lost to follow up, prior to this designation, the Investigator (or designee) must make every effort to make contact with the participant (e.g., telephone calls, certified letter to the participant's last known mailing address, or local equivalent methods, and efforts to reach the participant's emergency contact). The site will make 3 attempts to regain contact with the participant. These contact attempts must be documented in the participant's medical records.

Any participant who discontinues from the study will be asked to return to the clinic for an EOS visit that includes the assessments as shown in the schedule of assessments ([Table 3](#)). The reason and date for the participant's discontinuation from the study must be recorded in the eCRF.

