9. STUDY PROCEDURES

Assessments and their timing to be performed are outlined in the schedule of assessments ([Table 3](#)).

See Sections [10](#), [11](#), [12](#), and [13](#) for additional details regarding PK, PD, safety, and other assessments, respectively.

The Investigator may, at his or her discretion, arrange for a participant to have an unscheduled assessment, especially in the case of AEs that require follow up or are considered by the Investigator to be possibly related to the use of study treatment. The unscheduled visit page in the eCRF must be completed for all unscheduled assessments.

Table 3. Schedule of Assessments

Assessment	Screening	Euglycemic Clamp Procedure Treatment Periods 1-3 ¹			EOS Visit Within 2-11 Days After Last Administration of Study Drug
	-28 to -1 Days Prior to Treatment Period 1	Day -1	Clamp Procedure Starting the Morning of Day 1 for 12 Hours ²	Post- Clamp (Day 2)	
Informed consent	X				
Demographic data ³	X				
Alcohol and tobacco consumption patterns	X				
Medical and medications history ⁴	X	X			
Inclusion/exclusion criteria	X	X			
Admission to CRU ⁵		X			
Randomization			X ⁶		
Discharge from CRU				X	
Height/weight ⁷	X	X			
Physical examination ⁸	X				X
Vital signs ⁹	X		X	X	X
12-lead ECG	X				X
Hematology ¹⁰	X				X
Clinical chemistry ¹¹	X				X
Blood coagulation ¹²	X				
Serology tests (HBsAg, IgM anti-HBc, HCV, ¹³ HIV)	X				
Urinalysis ¹⁴	X				
Urine screen for drugs of abuse ¹⁵	X	X			
Alcohol breath test ¹⁶	X	X			
Human insulin antibodies	X				
Oral glucose tolerance test ¹⁷	X				
Study drug administration ¹⁸			Day 1 at time = 0 hours/0 min		
Injection site assessment ¹⁹			X		X
GIR			X		
Adverse events					→

Assessment	Screening	Euglycemic Clamp Procedure Treatment Periods 1-3 ¹			EOS Visit Within 2-11 Days After Last Administration of Study Drug	
	-28 to -1 Days Prior to Treatment Period 1	Day -1	Clamp Procedure Starting the Morning of Day 1 for 12 Hours ²	Post-Clamp (Day 2)		
Concomitant medications				→		
PK, PD, C-peptide, and glucose sampling (see Table 4)						

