## 21. Other assessments

The following assessments will only be presented in data listings for the SAF population:

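### The SAP keeps an ECG table by insulin product, but ECG is scheduled only at screening and at one end-of-study visit, so the table cannot separate the products

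*Protocol*

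**What the plan says.** **ECG grouping.** Protocol 14.5 states that the frequency of ECG abnormalities "will be summarized by treatment group and scheduled visits using counts and percentages". SAP 21.2 uses the same words. The synopsis (Safety row) names the grouping directly: original and change-from-baseline values, including "ECG parameters, will be summarized by insulin product and scheduled visits". In Protocol 14.5 the treatment groups are spelled out, for adverse events, as the three products.

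**ECG listing.** SAP 21, which covers 21.2, opens with "The following assessments will only be presented in data listings for the SAF population".

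**Laboratory grouping.** Protocol 14.5 plans laboratory data by treatment group and "scheduled visits using descriptive statistics, including mean values and mean change from screening values", with shift tables from screening to EOS. SAP 19.2 instead summarises haematology, chemistry, coagulation and urinalysis for each treatment sequence, by visit and time point, as actual values and change from baseline. Protocol 14 says the SAP prevails where the two differ.

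**Schedule (Protocol Table 3).** The 12-lead ECG, hematology and "Clinical chemistry" rows are marked at screening and in the column headed "EOS Visit Within 2-11 Days After Last Administration of Study Drug". The rows for "Blood coagulation" and urinalysis are marked at screening only.

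**Early withdrawal.** Protocol 8.4: "Any participant who discontinues from the study will be asked to return to the clinic for an EOS visit".

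**The concern.** In a three-period crossover, a by-product safety table is informative only if the measurement is taken after one product and before the next. Adverse events and period-level vital signs meet that condition. The ECG does not, because all three doses have been given before a completer's first post-dose ECG.

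A by-product ECG table would look like a comparison of NKF-INS(A) with its two references while resting on data that cannot make one. Similar columns could be read as reassurance. An abnormality could be placed under a product that did not cause it. Safety of NKF-INS(A) is a secondary objective, and Protocol 4.1 describes this as its first clinical study, so readers will look at that table.

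The programmer also has two incompatible instructions within SAP 21: list only, or tabulate by group.

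**Working it through.** The plan states no figure for this point, so there is nothing to reproduce. The check sets the schedule against the summary rules and then counts.

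**Step 1. Scheduled post-dose measurements per completer (Protocol Table 3).**

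| Assessment | Between products | At EOS | Grouping in Protocol 14.5 / synopsis | Grouping in SAP |
|---|---|---|---|---|
| 12-lead ECG | 0 | 1 | product | treatment group (21.2); listing only (21 opening) |
| Hematology | 0 | 1 | product | sequence (19.2) |
| Clinical chemistry | 0 | 1 | product | sequence (19.2) |
| Coagulation | 0 | 0 | product | sequence (19.2) |
| Urinalysis | 0 | 0 | product | sequence (19.2) |

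**Step 2. Can another rule fill the ECG gap?**
- SAP 18.2.3 assigns an event to the last treatment received before onset, but for adverse events only. No equivalent rule exists for ECG.
- SAP 6.1 keeps unscheduled measurements out of by-visit summaries, so an extra ECG taken in a treatment period would not enter the table.
- SAP 6.2 sets baseline before the first dose of any product, so the change from baseline at EOS is also a single value per participant.
- SAP 8 defaults to treatment sequence unless otherwise specified, and 21.2 does specify otherwise.

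**Step 3. What a by-product table would contain.** Inputs: six sequences allocated equally, 54 planned participants and at least 36 evaluable (Protocol 6.1). Assume equal numbers per sequence and that those counted received all three doses.

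*Option A, enter each EOS value under every product received:*
- 54 completers: 54 × 3 = 162 entries from 54 distinct values.
- 36 completers: 36 × 3 = 108 entries from 36 distinct values.
- The three columns are identical by construction.

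*Option B, assign each EOS value to the last product.* Each product is last in 2 of the 6 sequences:
- 54 completers: 54 × 2/6 = 18 per product. The other 54 − 18 = 36 exposures to that product have no ECG before the next dose.
- 36 completers: 36 × 2/6 = 12 per product. The other 36 − 12 = 24 exposures have none.
- Everyone in each column has also received the other two products, and the comparison is now between participants.

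**Step 4. Coagulation and urinalysis.** With no scheduled sample after screening, the change from baseline in SAP 19.2 and the shift to EOS in Protocol 14.5 have no scheduled follow-up value to use.

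**The case against.** The strongest reply is that the governing document has already dealt with most of this. Several parts of that reply stand.

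- **Laboratory data.** A reader of Protocol 14.5 might infer that by-product laboratory tables will be produced. The documents do not support that: SAP 19.2 uses treatment sequence, and the SAP prevails. A by-sequence EOS table does not assign a value to one product. What remains is a difference in wording between the two documents.
- **Every by-product table would misattribute.** This is too strong. A table openly labelled by last product received would be weak but not false. No document specifies one, however. The EOS value also follows all three products in completers only; someone who withdraws after period 1 has an EOS visit that follows one product.
- **QTcF categories.** A reader might take the QTcF change categories in SAP 21.2 as by-product too. The by-group sentence covers the frequency of abnormalities; no grouping is stated for the categories.
- **Treatment group is not defined in SAP 21.2, and the section opening says listings only.** Both are true. But the sentence is carried over unchanged from Protocol 14.5, where the groups are products, and the synopsis says insulin product. The listings-only opening contradicts 21.2 rather than settling the matter.
- **Clinically significant ECG findings are recorded as adverse events and tabulated by treatment of event.** This means a real finding would still be reported. It does not make the ECG table valid, and the adverse-event rule would itself place a finding first seen at EOS under the last product.
- **These are descriptive tables with no hypothesis test.** Agreed. This limits the consequence to the safety presentation.

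**Conclusion.** The point holds for ECG. SAP 21.2 retains a by-product summary that the visit schedule cannot support, gives no attribution rule, and conflicts with the opening of SAP 21. Under last-product attribution each product has 18 of 54 participants if all complete, or 12 of 36 at the minimum evaluable number, and all of them have also received the other two. Under repetition the columns are identical.

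For laboratory data the by-product wording is confined to the protocol and synopsis and is superseded. Separately, the coagulation and urinalysis change and shift summaries have no scheduled post-dose data.

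This rests on three assumptions: that treatment group in SAP 21.2 means insulin product, as in the protocol; that Table 3 is read correctly as marking ECG at screening and EOS only; and that completers are spread evenly over the sequences. Unequal completion would shift the counts but not the conclusion.

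The correction should be made, but it concerns descriptive safety output only. The primary PK/PD analyses, power and alpha are unaffected.

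**What to change.** 1. **SAP 21.2:** replace the treatment-group grouping with EOS ECG as change or shift from screening, overall and/or by treatment sequence. State the same grouping for the QTcF categories, and say that these data do not support a comparison of products.
2. **SAP 21 opening:** reconcile it with 21.2. A summary on the lines of item 1 or listings only would each cure the defect; choose one.
3. **Protocol 14.5 and synopsis:** align the laboratory wording with SAP 19.2 and the ECG wording with the corrected 21.2.
4. **Coagulation and urinalysis:** reconcile the planned change and shift summaries with Table 3, which has no post-dose sample for either.

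SAP 19.2 has no by-product wording to remove. No change is needed on this account to vital signs (SAP 20.2, by sequence) or injection-site scores (SAP 21.3, by type and timepoint).

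The cost is wording in the SAP, protocol and synopsis, and the same number of tables or fewer. The ECG and laboratory grouping changes need no new data.

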14.6. Other Analyses

All other safety variables will be listed.

14.7. Interim Analysis

No interim analysis is planned.

14.8. Data Monitoring Committee

Not applicable.

15. STUDY MANAGEMENT

15.1. Approval and Consent

15.1.1. Compliance with Laws and Regulations

This study will be conducted in full conformance with the ICH E6 guideline for GCP and the principles of the Declaration of Helsinki or all relevant laws and regulations of the country in which the research is conducted, whichever affords the greater protection to the individual.

The study will comply with the requirements of the ICH E2A guideline (Clinical Safety Data Management: Definitions and Standards for Expedited Reporting). Studies conducted in the EU or European Economic Area will comply with the EU Clinical Trial Regulation (CTR).

15.1.2. Institutional Review Board/Independent Ethics Committee

This protocol, protocol amendments (if applicable), Investigator's Brochure, the ICFs, recruitment material and participant information sheets, any information to be given to the participant, and relevant supporting information must be submitted to the IEC/IRB by the Principal Investigator (PI) and reviewed and approved by the IEC/IRB before the study is initiated; no participant may undergo any procedure for determining eligibility for this study until IEC/IRB approval is obtained.

The PI is responsible for providing written summaries of the status of the study to the IEC/IRB annually or more frequently in accordance with the requirements, policies, and procedures established by the IEC/IRB. Investigators are also responsible for promptly informing the IEC/IRB of any protocol amendments. The PI must receive approval/acknowledgement from the IEC/IRB before implementation of the amendment.

In addition to the requirements for reporting all AEs to the Sponsor, Investigators must comply with requirements for reporting SAEs to the local health authority and IEC/IRB.

Investigators may receive written investigational new drug safety reports or other safety-related communications from the Sponsor. Investigators are responsible for ensuring that such reports are reviewed and processed in accordance with health authority requirements and the policies and procedures established by their IEC/IRB and archived in the site's study file.

15.1.3. Informed Consent Process

15.1.3.1. Consent and Other Informational Documents Provided to Participants

Consent forms describing in detail the study intervention, study procedures, and risks are given to the participant and written documentation of informed consent is required before protocol-specific procedures are performed.

15.1.3.2. Consent Procedures and Documentation

Informed consent is a process that is initiated before the participant's agreeing to participate in the study and continues throughout the study participation. Consent forms will be IRB-approved, and the participant will be asked to read and review the document. The Investigator will explain the research study to the participant and answer any questions that may arise. A verbal explanation will be provided in terms suited to the participant's comprehension of the purposes, procedures, and potential risks of the study and of their rights as research participants. Participants will have the opportunity to carefully review the written

consent form and ask questions before signing. The participants should have the opportunity to discuss the study with their family or surrogates or think about it before agreeing to participate. The participant will sign the informed consent document before any procedures being done specifically for the study. Participants must be informed that participation is voluntary and that they may withdraw from the study at any time, without prejudice. A copy of the informed consent document will be given to the participants for their records. The informed consent process will be conducted and documented in the source document (including the date), and the form signed, before the participant undergoes any study-specific procedures. The rights and welfare of the participants will be protected by emphasizing to them that the quality of their medical care will not be adversely affected if they decline to participate in this study.

